6.6.2 Dietary Restrictions

6.6.2.1 Confinement Period

A standard diet will be designed by a dietician. For each meal, the caloric and fat content should be controlled in order to avoid “high-fat” diet. The FDA guidance on food-effect studies for bioequivalency testing identifies a “high-fat” diet as a diet which maintains approximatively 50 percent of total caloric content of the meal and is high in calories (approximately 800 to 1000 calories) (FDA, 2002).

In order to avoid any effect on assessment of BoExp, grilled or pan-fried meat, smoked pre-cooked meats (e.g., tuna, ham, corned beef, and meats), smoked bacon and sausage will not be permitted (Tiffany et al., 1991). In addition, to avoid any effect on the measurement of CYP1A2 activity, alcohol, broccoli, brussels sprouts, cauliflower, grapefruit, and xanthine-containing foods and beverages (coffee, tea, chocolate, cocoa, mate, guarana etc.) will be forbidden (Faber et al., 2004) (except for the intake of the caffeine tablet for CYP1A2 measurement). Consumption of quinine-containing drinks (e.g., tonic water) is not allowed.

Subjects are not allowed to bring their own food or beverages to the investigational site. Meals will be served according to the schedules provided in Section 9. Additional light snack, fruits, and raw vegetables can be distributed to the subjects without restrictions at any time during confinement as long as they fulfill the above requirements described in this section. Consumption of water is allowed as desired. The same menu and meal schedule will be administered uniformly for all subjects in all study arms. In addition for the purpose of the Ames test planned on Day 0 and Day 5, the menus served on Day-1 and Day 4 will be identical.

Fasting state has to be observed for at least 10 hours prior to blood draws for:

1. safety laboratory on screening, Day 0, Day 6
2. risk marker in serum/plasma/blood on Day 0 and Day 6.
3. serum/plasma bio-banking samples for further analysis of BoExp and risk markers at the Screening Visit, on Day 0, Day 6.
4. blood bio-banking for transcriptomics on Day 0, Day 6.

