9.2 Confinement Period (Days -2 to 6)

9.2.1 Admission (Day -2)

The procedures of Day -2 can be performed in order deemed most practical, except the product test which will be the last assessment prior to enrolment after all eligibility criteria have been met. Subjects will attend the investigational site in at least 10-hour fasting state for clinical laboratory to be assessed.

Table 8 shows the assessments that will be performed at Admission (Day -2):

Table 8. Time Schedule – Day -2

Time	Blood sample	Procedures	Additional information
Start of procedure		Admission	
Time of admission-06:30 PM		AE/SAE recording; Concomitant medication	All day
Time of admission-06:30 PM		Urine pregnancy test (all females only)	
Time of admission-06:30 PM		Advice on the risk of smoking and debriefing	
Time of admission-06:30 PM		Smoking history	
Time of admission-06:30 PM		Willingness to abstain from smoking for up to 90 days	
Time of admission-06:30 PM		Urine drug screen	
Time of admission-06:30 PM		Urine cotinine screening test	
Time of admission-06:30 PM		Alcohol breath test screen	
Time of admission-06:30 PM		CO breath test	Irrespective of the time of product use
Time of admission-06:30 PM		Vital signs (blood pressure, pulse rate, respiratory rate)	At least 5 minutes in supine position prior to measurement
Time of admission-06:30 PM		Physical examination, and weight, waist circumference, and BMI	Weight and waist circumference to be evaluated also as risk markers
Time of admission-06:30 PM		Inclusion/exclusion criteria	
Time of admission-06:30 PM		Identification of current mCC brand	

Data and information contained in this document are considered to constitute trade secrets and confidential commercial information, and the legal protections provided to such trade secrets and confidential information are hereby claimed under the provisions of applicable law. No part of this document may be publicly disclosed without the written consent of Philip Morris Products S.A.

Time	Blood sample	Procedures	Additional information
Start of procedure		Admission	
Time of admission- 06:30 PM		Product test of THS 2.2 Menthol	Must be done only after the pregnancy test is confirmed negative. The product test is the last assessment prior to enrolment.
Time of admission- 06:30 PM		Enrolment	After all inclusion and exclusion criteria have been satisfactorily met
		Preference product question	Has to be done after enrolment
Before 09:00 PM		Dinner	
11:00 PM		End of smoking period	

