In the afternoon prior to discharge of Day 91		Physical examination, including weight calculated BMI, and waist circumference	Weight and waist circumference to be evaluated also as risk markers

Time	Blood sample	Procedures	Additional information
Start of procedure		Day 91	
In the afternoon prior to discharge of Day 91		Vital signs (blood pressure, pulse rate, respiratory rate)	At least 5 minutes in supine position prior to measurement
In the afternoon prior to discharge of Day 91		ECG	At any time during the day Systolic and diastolic BP to be evaluated also as risk marker
In the afternoon prior to discharge of Day 91		Urine safety analysis and pregnancy test	At least 10 minutes in supine position prior to recording
In the afternoon prior to discharge of Day 91		Advice on the risk of smoking and debriefing	

Time of Discharge On Day 91

Abbreviations: 8-epi-PGF2 α = 8-epi-prostaglandine F2 α ; 11-DTX-B2 = 11-dehydro-thromboxane B2; AE = adverse event;; BMI = body mass index; BoExps = biomarkers of exposure; mCC = conventional cigarette(s); CO = carbon monoxide; COHb = carboxyhemoglobin; CYP = cytochrome P450 enzyme; ECG = electrocardiogram; HbA1c = hemoglobin A1c; hs-CRP = high-sensitive C-reactive protein; HDL = high density lipoprotein; HST = human smoking topography; LDL = low density lipoprotein; MCEQ = Modified Cigarette Evaluation Questionnaire; MNWS = Minnesota Nicotine Withdrawal Scale; QSU = Questionnaire of Smoking Urges; SAE = serious adverse event; sICAM-1 = soluble inter-cellular adhesion molecule; TG = triglycerides; THS = tobacco heating system; WBC = white blood cell count.

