12.6.2.5 Risk Markers

The risk markers are:

- Systolic and diastolic blood pressure on Day 0, Day 6, Day 30 Visit, Day 60 Visit, and Day 90 Visit.
- hs-CRP, homocysteine, blood glucose, LDL, HDL, TG, and TC in serum on Day 0, Day 30 Visit, Day 60 Visit, and Day 90 Visit.
- Fibrinogen in plasma on Day 0, Day 30 Visit, Day 60 Visit, and Day 90 Visit.
- HbA1c in blood on Day 0 and Day 90 Visit.
- sICAM-1 in serum on Day 0, Day 6, Day 30 Visit, Day 60 Visit, and Day 90 Visit.
- WBC and platelet count in blood on Day 0, Day 6, Day 30 Visit, Day 60 Visit, and Day 90 Visit.
- 8-epi-PGF2 α and 11-DTX-B2 in 24 hour urine on Day 0, Day 5, Day 30 Visit, Day 60 Visit, and Day 90 Visit (expressed as concentration adjusted for creatinine).
- Body weight and waist circumference on Day -2 and Day 90 Visit.

The results along with the changes from baseline will be listed and summarized. In addition line graphs will be produced for product means (and 95% CI) over all timepoints.

The analysis will compare the results on Day 90 between the THS 2.2 Menthol and mCC arms, and between the THS 2.2 Menthol and SA arms for the FAS and PP set. An ANCOVA model will be used with terms for Baseline, sex, average daily mCC consumption over the last 4 weeks as reported during screening and randomization arm. No adjustment will be made for multiple comparisons.

Blood pressure, HbA1c, LDL, HDL, TG, TC, WBC, body weight and waist circumference will be analyzed in the regular scale. 8-epi-PGF2 α , 11-DTX-B2, sICAM will be analyzed in the logarithmic scale. Other risk markers will be logarithmically transformed prior to analysis if there is evidence of non-normality by means of Shapiro-Wilks test.

The SAS code will be the same as described in Section 12.6.1.1 “Analysis of Biomarkers of Exposure for Primary Objectives”.

LS means for each product along with the difference (THS 2.2 Menthol - mCC) or ratio (THS 2.2 Menthol : mCC) and 95% CI will be presented in the tables along with a forest plot of the results.

If there are any 11-DTX-B2 assessments performed within 5 half-lives since the use of a concomitant medication affecting the production of 11-DTX-B2, the analysis will be repeated by excluding these assessments for both the PP Set and FAS

All tables, figures and analyses will be produced for the FAS and PP set. Figures will be produced for the PP Set.

The data will be presented in the below outputs:

TFL number	Title
FIGURES	

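### Weight and waist circumference are not measured under matched conditions on Day -2 and Day 91, so within-arm 90-day changes can be shifted upward; the between-arm contrasts are not biased

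*Protocol*

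**What the plan says.** **Day -2 (Protocol 9.2.1, Table 8).** The section opens with "Subjects will attend the investigational site in at least 10-hour fasting state for clinical laboratory to be assessed". The row "Physical examination, and weight, waist circumference, and BMI" carries the window "Time of admission-06:30 PM" and is marked as also serving the risk markers. The order of the day is left open: "The procedures of Day -2 can be performed in order deemed most practical", except that the product test comes last before enrolment. Dinner is the only meal in the table.

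**Day 91 (Protocol 9.3, Table 18).** A fasting blood draw is scheduled, then breakfast before 10:00 AM. The row "Physical examination, including weight calculated BMI, and waist circumference" is timed for the afternoon, before the subject leaves. No lunch is listed that day.

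**Fasting rules.** Protocol 7.5.2.1 applies the 10-hour fast only to risk markers measured in blood, serum or plasma, so weight and waist fall outside it.

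**Analysis (SAP 12.6.2.5).** The pair of readings is "Body weight and waist circumference on Day -2 and Day 90 Visit". The SAP states: "The results along with the changes from baseline will be listed and summarized". Figures 15.1.2.4.1 and 15.1.2.4.2 plot mean percent change from baseline with 95% CI for each arm. The inferential comparison is between arms at Day 90, by ANCOVA adjusted for baseline. SAP 12.6.4.4.2 also describes weight, waist, BMI and BMI category at Baseline and Day 90.

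**The concern.** A change from baseline is interpretable only if both readings are taken in the same state. Here the later reading is always after food, while the earlier one is taken in subjects told to arrive fasted. Any food and fluid carried at the second weighing but not at the first is counted as 90-day change.

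Within-arm change has a use in this study. Protocol 4.2 includes SA as a reference point so that the course of the risk markers under THS 2.2 Menthol can be set beside it. It selects body weight because abstinence is expected to raise it (a mean 4.5 kg at 12 months, most of it in the first 3 months). An upward shift runs in the same direction as that expected signal. It could give an unchanged mCC arm an apparent gain and make the THS and SA changes look more alike than they are.

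**Working it through.** The documents give no SD, effect size, power or meal effect for weight or waist, so there is no stated figure to reproduce. The check sets the schedules side by side and then works out what a mismatch would do.

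**1. The two readings**

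| | Day -2 | Day 91 |
|---|---|---|
| Arrival or morning state | told to arrive fasted at least 10 h | fasted for the blood draw |
| Listed meal before the reading | none (dinner only, before 09:00 PM) | breakfast, before 10:00 AM |
| Time of reading | any time up to 06:30 PM, free order | afternoon |
| Fed or fasted state required for weight and waist | none | none |

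**2. Size of the within-arm shift.** Let m be the meal effect on weight (kg), assumed the same whenever a subject is fed, and f the share already fed when weighed on Day -2. The mean added at Day 91 is m and at Day -2 is m·f, so

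apparent change = true change + m − m·f = true change + m(1 − f).

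**3. Simulation of the planned ANCOVA.** Terms were baseline and arm; the sex and consumption terms were left out. Planned sizes are 80:40:40. Assumed, not from the documents: baseline mean 62 kg and SD 10 kg, noise SD 1.5 kg, true changes 0 (mCC), 0.5 (THS) and 1.5 kg (SA). There were 2,000 repetitions per scenario.

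| m (kg) | f | Apparent mCC change | THS − mCC (true 0.50) | THS − SA (true −1.00) |
|---|---|---|---|---|
| 0 | 0 | 0.004 | 0.496 | −0.997 |
| 0.3 | 0 | 0.306 | 0.500 | −1.000 |
| 0.3 | 0.5 | 0.158 | 0.494 | −0.991 |
| 0.5 | 0 | 0.507 | 0.486 | −1.015 |
| 0.5 | 0.5 | 0.249 | 0.503 | −0.993 |
| 1.0 | 0 | 1.005 | 0.494 | −1.009 |
| 1.0 | 0.5 | 0.509 | 0.495 | −0.995 |
| 1.0 | 1 | −0.004 | 0.503 | −1.003 |

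The mCC column follows m(1 − f). The contrasts do not move, for two reasons. The Day 91 shift is the same in every arm, so the intercept absorbs it. The Day -2 state is set before randomisation on Day 0, so f does not depend on arm.

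**4. When the shift would show in an interval.** For an arm of 40 with an assumed SD of change of 2 kg, SE = 2/√40 = 0.32 kg. A net shift above 1.96 × 0.316 = 0.62 kg would then move the expected 95% CI of an unchanged arm off zero. With SD 1.5 kg, SE = 1.5/√40 = 0.24 kg and the threshold is 1.96 × 0.237 = 0.46 kg.

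**5. Comparing trajectories.** With the illustrative true changes, THS is 0.5/1.5 = 33% of SA. A common shift of 0.5 kg gives 1.0/2.0 = 50%; a shift of 1.0 kg gives 1.5/2.5 = 60%. The difference stays at 1.0 kg throughout.

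**6. Two statements that do not fit together**
- *Day -2 fasting.* Section 9.2.1 justifies the fast by the clinical laboratory, but Table 8 has no laboratory draw, and Section 6.6.2.1 lists fasting for "safety laboratory on screening, Day 0, Day 6" without Day -2.
- *Weight baseline day.* Appendix 1 footnote b, repeated in the SAP appendix, names Day 0. Section 7.5.2.1 and SAP 12.6.2.5 name Day -2, and Section 7.4.8 schedules no weight on Day 0.

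**The case against.** The strongest reply is that a fasted baseline weighing is never established. The fasting sentence may be misplaced, since the Screening section has the same instruction and does include a draw. Even if subjects arrive fasted, the window runs to 06:30 PM, the order is free, and Section 6.6.2.1 allows snacks at any time in confinement. Fasted arrival is not fasted weighing. **This stands.** It means the shift may be anything from zero to m, not that the readings are matched. A mixture of fed and fasted subjects at baseline also adds some noise.

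Second, the objective is comparative, the planned test is between arms, and the concurrent mCC arm controls for a shift common to all arms. **This stands in full** for the inference. It does not cover the within-arm summaries and plots that the SAP also commits to.

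Third, matching only Day -2 and Day 91 leaves other weights unmatched. The Day 30 and Day 60 weights are taken between 02:30 and 07:00 PM, after the lunch slot, and the Day 6 weight is listed after breakfast. **This is correct** for the safety series in SAP 12.6.4.4.2. For the risk-marker analysis, Day -2 and Day 91 are the only weight and waist time points.

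A reader might go further and infer that every arm's change does contain a meal artefact and that unchanged mCC smokers will appear to gain. The documents do not support that: they fix neither f nor m, and breakfast is the only meal listed before the Day 91 reading.

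**Conclusion.** The two readings that define the 90-day change in weight and waist are not taken under matched conditions. The reported within-arm changes, their intervals and plots, and the BMI category counts can be shifted upward in all arms. For weight the shift lies between zero and the full meal effect: 0 to 1.0 kg if m is 0.3 to 1.0 kg. This rests on an assumed m, an unknown f, and the same meal effect whenever a subject is fed. The SDs behind the interval thresholds of 0.46 and 0.62 kg are assumptions too. No size can be given for waist circumference or for the BMI category counts.

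It would be wrong to conclude that the THS versus mCC or THS versus SA comparison is biased. In all simulated scenarios the contrasts stayed at their true values within simulation error. The importance is minor: it affects descriptive output on two of many secondary risk markers.

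**What to change.** - **Table 18 (and Section 7.4.8):** take Day 91 weight and waist in the morning with the existing fasting blood draw, before breakfast.
- **Table 8:** take Day -2 weight and waist on arrival, before any food.
- **In the same edit:** reconcile the Day -2 fasting sentence in Section 9.2.1 with Section 6.6.2.1 and Table 8. Also reconcile the Day 0 weight baseline in Appendix 1 footnote b (and its copy in the SAP appendix) with Day -2 in Section 7.5.2.1 and SAP 12.6.2.5.

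The cost is two schedule rows and the wording corrections, with no extra visit, staff or procedure. With both readings before food, the expected meal shift is zero and the contrasts are unchanged. If the Day 6, Day 30 and Day 60 weights are to be comparable as well, their rows would need the same treatment; the two-row change does not do that.

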9.4 Safety Follow-up Period

All subjects participating in the product trial on Day -2 and are not enrolled into the study will enter a 28-day safety follow-up period.

After subjects have completed the Day 91 safety assessments (or if they are prematurely withdrawn from the study), they will enter a 28-day safety follow-up period.

During the 28-day safety follow-up period, there will be spontaneous reporting by the subject of new AEs and new SAEs. Any ongoing AEs/SAEs will be actively followed-up by the site.

Any AEs or SAEs that are ongoing at the end of the 28-day safety follow-up period will be handled as described in Section 8.

9.5 Early Termination Procedures

The safety assessments as described on Day 6 will be performed as early termination procedures (see Section 9.2.4).

10 CONTROL AND QUALITY ASSURANCE

10.1 Monitoring

The Clinical Research Associate (“Monitor”) will be responsible for the monitoring of the study. Monitoring will be performed according to CRO’s Standard Operating Procedure (SOPs) and as per the agreed monitoring plan with the Sponsor.

The Principal Investigator/head of the investigational site shall permit the Monitor to review study data as frequently as considered necessary to ensure that data are being recorded in an adequate manner and that protocol adherence is satisfactory.

The Investigator shall access medical records for the Monitor in order that entries in the eCRFs may be verified. The Investigator, as part of their responsibilities, is expected to ensure that the study adheres to GCP requirements.

An Investigator’s meeting will be held prior to the site initiation visit. During this meeting, the general training of the study procedures and specific training on selected procedures will be done and documented.

Subsequent to the Investigator’s meeting, and before the first subject is screened into the study, site initiation visit will be conducted by the Monitor and, if necessary, with Sponsor or its authorized representative. The purpose of the site initiation visit will be detailed in the monitoring plan.

During the study, the Monitor will have regular contact with the study site, including interim monitoring visits. The purpose of these visits is described in the monitoring plan.

Communication by telephone, mail, and e-mail may be used as needed to supplement site visits. The Investigator and study collaborator will cooperate with the Monitor, provide all appropriate documentation, and will be available to discuss the study.

The Monitor and the Sponsor’s personnel will be available between visits, should the Investigator or other study collaborator at the sites need information and advice.

Site visits will be made at regular intervals during the study. The frequency of the monitoring visits will be defined in the monitoring plan agreed with the Sponsor.

The Investigator or a designated member of the Investigator’s study collaborator must be available during the monitoring visit to review the data and resolve any queries, and to allow direct access to the subject’s records for source data verification.

10.2 Training of Study Collaborators

A formal meeting (Investigator's meeting) will be conducted prior to site initiation. During this meeting, the Sponsor or its authorized representative will discuss the requirements of the clinical study protocol and related documents and will also provide training in the relevant systems and other study-specific procedures. The activities of the Investigator's meeting will be described in the monitoring plan.

In addition to the Investigator meeting, the PI will ensure that appropriate training relevant to the study is provided to all study collaborator involved in the study, and that any new information relevant to the performance of this study is forwarded to the study collaborator involved in a timely manner. The record of all individuals involved in the study will be maintained in the Site Investigator File.

10.3 Audits and Inspections

Good Clinical Practice regulations require that there are independent inspections of clinical program activities. Such inspections may be performed at any time before, during and/or after the study.

Authorized representatives of the Sponsor, regulatory agencies and/or an IRB may perform audits or inspections, including source data verification. The purpose of an audit or inspection is to systematically and independently examine all study-related activities and documents to determine whether these activities were conducted, and data were recorded, analyzed, and accurately reported according to the protocol, ICH/GCP guidelines, and any applicable regulatory requirements. The Principal Investigator/head of investigational site will contact the Sponsor or the authorized representative immediately, if contacted by a regulatory agency about an inspection at their site.

The Investigator and study collaborator are responsible for maintaining a comprehensive and accurate filing system of all study-related documentation that will be suitable for inspection at any time by the Sponsor, its authorized representative, and/or regulatory agencies. In signing this protocol, the Investigator understands and agrees to provide access to the necessary documentation and files.

11 DATA MANAGEMENT ACTIVITIES

All Data Management Activities will be described in detail in the Data Management Plan and documents specified therein.

11.1 Data Capture

11.1.1 Case Report Forms and Study Records

With the exception of the subject reported outcome data, all results from the clinical assessments will be recorded in the Source Documents by the Investigator or authorized designee and then captured in the eCRFs at the study site. The subject questionnaires and the VAS will be entered by the subject directly in the electronic patient reported outcomes device or on paper copy. Trained study personnel will be responsible for capturing the data from the observations, tests, and assessments specified in the protocol in the source documents and then transferring the data into the eCRF according to the eCRF Completion Guidelines.

The Principal Investigator has ultimate responsibility for the collection and reporting of all data related to the clinical study and ensuring that the data are accurate, authentic/original, legible, timely (contemporaneous), enduring, and available when required. The eCRF must be signed by the Investigator to attest that the data contained in the eCRF are true and accurate. Any corrections made to Source Documents must be clearly recorded, without obscuring the original values and be accompanied by the date of change, reason for change, and identification of the person making the change. The eCRF for each subject will be checked against the Source Documents at the study site by the CRA. Instances of missing or unclear data will be discussed with the Investigator for resolution. An eCRF will be generated for all subjects that sign the informed consent.

For the ePRO device, all subject reported outcome data will be provided in English and instructions will be provided in the subject's local language.

